**Exclusion criteria:**

1. Patients with age above 60 or below 18 years old.
2. Patients with severe non proliferative diabetic retinopathy up to advanced proliferative diabetic retinopathy.
3. Patients diagnosed with type 1 DM.
4. Patients with malignant tumors.
5. Patients with end stage renal disease and end stage liver disease.
6. Patients with history of myocardial infarction.
7. Patients with recurrent attacks of hypoglycemia and hypoglycemia unawareness.

## **Sampling Method:**

Purposive sampling

## **Sample Size:**

The study will be conducted on 80 subjects.

## **Ethical and Safety Consideration:**

This study will be done after approval of the Ethical Committee of the Department of Internal Medicine, Faculty of Medicine, Ain Shams University. Informed consent will be taken from all participants before recruitment in the study, and after explaining the purpose and procedures of the study. The investigator will retain the original signed informed consent form. All data will be collected confidentially. The study will be based on the investigator self-funding.

## **Study procedures and interventions:**

1. After approval of study protocol, patients will be enrolled into the study according to inclusion and exclusion criteria.
2. All participants will sign written informed consent that is approved by the local ethics committee.
3. All patients will be subjected to:
  - **Detailed history taking of the patient medical condition.**
  - **Anthropometric and blood pressure measurements:**
    - ✓ Weight and height of all patients will be measured using a calibrated scale. Body mass index (BMI) will be calculated by dividing weight in kilograms by height in meters squared.

- ✓ Blood pressure will be measured in both standing and seated position after a 5-min rest using an aneroid sphygmomanometer and stethoscope.

- ✓ Basal heart rate measurement

➤ **Biochemical assays:**

- ✓ Laboratory measurements will include:
  - ❖ Fasting, 2 hour post prandial glucose levels and HbA1C.
  - ❖ Kidney function tests including serum urea and creatinine.
  - ❖ Albumin/creatinine ratio.
  - ❖ Estimated GFR calculation using MDRD 4 variable equation.
  - ❖ Complete blood count.

➤ **Fundus examination using Optomed aurora portable fundoscopy.**

➤ **Neurological assessment usingDN4 (Douleur Neuropathique 4 questions).**

- **Labs, neurological and Fundus examination will be done at time of recruitment and 6 months following glycemic control.**

▪ **Outcomes:**

Effect of tight glycemic control on microvascular complications of Diabetes.

▪ **Statistical analysis:**

To summarize characteristics of study patients based on TyG quartiles, one-way analysis of variance (ANOVA) and chi-square ( $\chi^2$ ) tests will be used, where appropriate. To determine the association of liver fibrosis with TyG, multivariable-adjusted odds ratios (ORs) will be applied. Two-sided significance at  $P < 0.05$  will be significant.

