## What is already known on this subject? AND

## What does this study add?

Near normalization of blood glucose levels has been known to reduce the long-term risk of diabetic retinopathy. However, transient worsening of preexisting retinopathy has also been demonstrated when glucose control is intensified (**Bethel A. et al., 2021**).

The pathophysiology of this phenomenon is not well understood. Furthermore, the circumstances under which it appears remain to be not fully elucidated. Since its discovery, early worsening has been described in patients with type 1 and type 2 diabetes, including those undergoing various diabetic therapies, those who have undergone bariatric surgery, and pregnant women (**Feldman-Billard et al., 2018**).

Hence, this study will assess the relationship between the glycemic control in patients with diabetes mellitus and the contemporary statements on the value of tight glycemic control, when compared with less tight control with regard to microvascular outcomes including diabetic retinopathy, nephropathy and neuropathy.

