## 2.AIM / OBJECTIVES

This randomized controlled study will examine the relation between tight glycemic control and microvascular complications of Diabetes in comparison with patients with good (less tight) glycemic control.

**Research question:** Does tight glycemic control worsens microvascular complications of Diabetes?

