### 3.METHODOLOGY:

#### **Patients and Methods/ Subjects and Methods/ Material and Methods**

- **Type of Study:**

Randomized controlled trial.

- **Study Setting:**

The study will be conducted at Ain Shams University Hospitals “outpatient diabetes clinic and inpatient department.”

- **Study duration:**

This study will be conducted during the period from May 2022 to October 2023

- **Labs (see later), thorough clinical examination with special emphasis on microvascular complications (neurological and Fundus examination) will be done for every patient at time of recruitment and 6 months following glycemic control.**

- **Study Population:**

- 80 subjects with uncontrolled Diabetes Mellitus with HbA1c 8% or above all will receive standard medical care (nutritional therapy and pharmacological therapy) and will be divided into two groups:
  - (a) Group (A) will undergo tight glycemic control (HbA1c <7%) done by nutritional education and medication adjustment.
  - (b) Group (B) will undergo conventional glycemic control (HbA1c <7.5 %).

Subjects will be collected from patients with Diabetes Mellitus referred to Ain Shams University Hospitals for evaluation with the following criteria:

- **Inclusion criteria:**

1. Both sexes.
2. Age 18-60years old.
3. Patients diagnosed with Diabetes Mellitus (Type 2) according to ADA guidelines.
4. Patients willing to participate after signing a written consent to be enrolled in the study after being explained to them in an interview.
5. Diabetic patients with mild and moderate non proliferative diabetic retinopathy

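### The protocol's only outcome is a concept covering eye, kidney and nerve; no primary measure and no definition of worsening is named, so the deciding result can be chosen after the data are seen.

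*Protocol*

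**What the plan says.** The Aim is to "examine the relation between tight glycemic control and microvascular complications of Diabetes" against less tight control, and it is followed by one yes/no question: "Does tight glycemic control worsens microvascular complications of Diabetes". The Outcomes item, under Study procedures and interventions, repeats the aim as "Effect of tight glycemic control on microvascular complications of Diabetes" and adds nothing.

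The introductory section on what the study adds speaks of "microvascular outcomes including diabetic retinopathy, nephropathy and neuropathy". That gives three domains in no stated order of importance.

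Study procedures and interventions lists the measurements: a fundus examination, the DN4 questionnaire, serum urea and creatinine, albumin/creatinine ratio and estimated GFR. Labs, neurological and fundus examinations are scheduled at recruitment and 6 months after glycemic control. The instruments and timing are therefore stated. None of these measures is called primary, and none has a threshold for worsening.

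The Statistical analysis paragraph describes ANOVA and chi-square tests across TyG quartiles and odds ratios for liver fibrosis, then sets two-sided significance at P < 0.05. It mentions neither the randomised groups nor any microvascular measure. The Sample Size section gives 80 subjects, with no endpoint attached.

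**The concern.** One question is asked of a concept that at least six listed measures could represent. If nothing fixes beforehand which of them gives the answer, the choice can be made by looking at the results. A worse DN4 score, a higher albumin/creatinine ratio or a worse fundus grade could each be presented as the answer.

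Two things are at stake. If any one significant domain is taken as showing harm, the chance of a false claim exceeds that of a single named test. And a reader of the final report could not tell a planned conclusion from a selected one.

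The omission is not one that a statistical analysis plan would normally repair. Such a plan says how the primary outcome is analysed; which outcome answers the research question belongs in the protocol. Here the protocol has an Outcomes item and fills it with a restatement of the aim.

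**Working it through.** **Can the primary outcome be inferred from the rest of the protocol?**

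- *Rationale.* The introduction says that "transient worsening of preexisting retinopathy has also been demonstrated when glucose control is intensified". This points to the eye.
- *Eligibility.* The inclusion list has "Diabetic patients with mild and moderate non proliferative diabetic retinopathy" and the exclusion list has "Patients with severe non proliferative diabetic retinopathy up to advanced proliferative diabetic retinopathy". Entry is by retinopathy grade, which again points to the eye.
- *Assessments.* The Methodology section stresses the neurological and fundus examinations together. This points to two domains.
- *Introduction, last paragraph.* All three domains are listed as outcomes.
- *Sample size.* 80 is given without effect size, event rate, SD or power. It cannot be reproduced, so the intended endpoint cannot be recovered from it.
- *Statistics paragraph.* It concerns other variables altogether.

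The text leans towards retinopathy but never names it.

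**Size of the consequence (illustration).** The protocol states no selection rule, so these inputs are assumptions: no true effect; three tests, one per domain named in the introduction; each at two-sided 0.05; any significant domain counted; jointly normal test statistics with a common pairwise correlation.

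Independent tests:

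- Harm only: 1 − 0.975³ = 1 − 0.9269 = 0.0731
- Either direction: 1 − 0.95³ = 1 − 0.8574 = 0.1426

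Correlated tests, by numerical integration over the shared factor u, with c = 1.96 and correlation ρ:

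- Harm only: 1 − ∫ φ(u) Φ((c − √ρ·u)/√(1 − ρ))³ du
- Either direction: the same, with the cubed term replaced by the probability of lying between −c and c given u

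| Correlation | False harm | False claim, either direction |
|---|---|---|
| 0 | 7.3% | 14.3% |
| 0.5 | 6.3% | 12.5% |
| 0.8 | 4.9% | 9.8% |
| One named test | 2.5% | 5.0% |

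Counting the six listed measures instead (fundus, DN4, urea, creatinine, albumin/creatinine ratio, eGFR), the independent case gives 1 − 0.975⁶ = 14.1% and 1 − 0.95⁶ = 26.5%. Several of these are closely related, so independence is an upper illustration there.

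**Power for one yes/no primary.** Assumptions: equal allocation (40 per group; the ratio is not stated), no dropout, uncorrected chi-square test, exact binomial calculation, and assumed worsening rates.

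| Rates compared | Two-sided 0.05 | Two-sided 0.0167 (0.05/3) |
|---|---|---|
| 10% vs 20% | 24.7% | 11.6% |
| 10% vs 30% | 63.2% | 43.8% |

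The actual size of this test at 10% vs 10% is 5.9%, so the 0.05 column is slightly generous.

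**The case against.** **The statistical analysis plan may deal with it.** This stands for part of the matter. How the significance level is shared across domains, and how a mixed pattern is read, are commonly left to that plan, which is not available here. It does not stand for the choice of primary outcome.

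**The error rates rest on a rule the protocol does not contain.** True. Nothing says that any one significant domain will be taken as the answer, and nothing shows an intention to report selectively. Every patient is to have all assessments at both times. The figures show what the open wording permits, not what the investigators plan. The count of three is also a choice, since the kidney alone has four listed measures.

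**Retinopathy is evidently the primary.** The rationale and eligibility support this reading, but the joint emphasis on neurological and fundus examination and the unranked list of three domains prevent it from being taken as settled.

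**A stronger reading to avoid.** A reader might infer that contradictory answers across domains would be common, because three estimates often differ in sign when there is no effect. Differing signs without significance would simply be read as no demonstrated effect. A real conflict needs one domain significantly worse and another significantly better. For three independent tests that has probability 1 − 2(0.975³) + 0.95³ = 1 − 1.8537 + 0.8574 = 0.4%, and with positive correlation it almost vanishes. The concern is selection of the deciding domain, not frequent contradiction.

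A reader might also take P < 0.05 as the planned threshold for each domain. The sentence closes a paragraph about TyG and liver fibrosis, so the protocol does not say that.

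**Conclusion.** The concern holds. The Outcomes item names a concept, the concept covers three unranked domains, worsening is undefined in all of them, and the only statistical paragraph describes different variables. The result that answers the research question can therefore be chosen after the data are seen, and as written the protocol contains no between-group analysis of any microvascular measure.

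Under the stated assumptions, the freedom to count any of three domains raises false harm from 2.5% to between 4.9% and 7.3%, roughly two to three times. The textual gap itself depends on no assumption; the error rates do. This should be corrected before any between-group comparison is made, because naming the outcome afterwards cannot undo the selection.

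**What to change.** **Name one primary outcome in the Outcomes item, before any between-group comparison.** The candidate with most support in the protocol is worsening of retinopathy grade on fundus examination from recruitment to 6 months, compared by randomised group. State the grading scale, the change that counts as worsening, and how two eyes are handled. The investigators should confirm that this is the outcome they intend. The kidney measures and DN4 then become secondary.

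**Replace the TyG and liver-fibrosis text** under Statistical analysis with the between-group test of that outcome at two-sided 0.05. Otherwise the named primary would have no stated analysis.

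**If all three domains are meant to be co-equal** and no statistical analysis plan sets a multiplicity rule, name one measure per domain and state the rule, for example Holm or Bonferroni at 0.0167 each. With Bonferroni and independent tests, false harm returns to 2.5%.

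**Cost.** Wording, plus recording a retinopathy grade at the 6-month fundus examination. That examination is already planned, but no grading scale or 6-month grade is mentioned. With one primary, a lone kidney or DN4 result is no longer confirmatory. Power may be limited: about 25% for 10% vs 20% and 63% for 10% vs 30%, falling to about 12% and 44% per domain under the three-domain Bonferroni option. Under either option the protocol should say that a non-significant result will not be read as absence of harm.

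### The statistical analysis paragraph describes a study of TyG and liver fibrosis; neither stated analysis compares Group A with Group B on a microvascular outcome

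*Protocol*

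**What the plan says.** The research question in 2. Aim / Objectives is "Does tight glycemic control worsens microvascular complications of Diabetes". The opening section (What does this study add?) sets tight against less tight control "with regard to microvascular outcomes including diabetic retinopathy, nephropathy and neuropathy". The Methodology section calls the study a randomised controlled trial and allocates 80 patients to Group A (tight control) or Group B (conventional control). The Outcomes line gives the effect of tight control on microvascular complications, and the assessments are timed as follows: "Labs, neurological and Fundus examination will be done at time of recruitment and 6 months following glycemic control".

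The Statistical analysis paragraph then names two analyses:

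- The first is descriptive and begins "To summarize characteristics of study patients based on TyG quartiles, one-way analysis of variance (ANOVA"; it adds chi-square tests.
- The second is inferential: "To determine the association of liver fibrosis with TyG, multivariable-adjusted odds ratios (ORs) will be applied".

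The paragraph closes with a two-sided 0.05 significance level. The Statistical Package section adds only the software.

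**The concern.** Neither the grouping variable (TyG quartile) nor the dependent variable (liver fibrosis) has any connection to the trial's aim, arms, outcome or measurements. The paragraph reads as though carried over from another study.

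An analyst who followed it would never produce the contrast the trial was randomised to estimate. An analyst who set it aside would choose outcome, time point, model and effect measure with nothing in this document to constrain the choice. Several microvascular measures are available, none is ranked, and the 0.05 level is tied to no endpoint. Any later A-versus-B result could then have been selected from several, and the protocol could not show otherwise.

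**Working it through.** The claim concerns which analyses are specified and disputes no figure, so the check is a comparison of sections and a count of terms.

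**1. What the trial needs against what the paragraph supplies**

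| Element | Elsewhere in the protocol | Statistical analysis paragraph |
|---|---|---|
| Comparison | Group A v Group B (2 arms) | TyG quartiles (4 levels) |
| Outcome | Retinopathy, nephropathy, neuropathy | Liver fibrosis |
| Measures | Fundus examination, albumin/creatinine ratio, eGFR, DN4 | None of these named |
| Timing | Recruitment and a 6-month follow-up | None stated |

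The paragraph therefore names 0 of 2 arms, 0 of 3 complications and 0 of these 4 measures. Serum urea and creatinine are also on the laboratory list; the paragraph does not name them either.

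**2. Where the paragraph's own terms occur**

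- TyG: 2 mentions, both in this paragraph, with no definition.
- Liver fibrosis: 1 mention, in this paragraph.
- Other mention of the liver: 1, in the exclusion criterion "Patients with end stage renal disease and end stage liver disease". This is an eligibility rule and measures nothing as an outcome.
- Triglycerides: 0 mentions.

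**3. Could the stated analyses be run on the planned data?** The listed assessments are history, weight, height, blood pressure, heart rate, fasting and post-prandial glucose, HbA1c, urea, creatinine, albumin/creatinine ratio, eGFR, blood count, fundus examination and DN4. None is a fibrosis measure, so the odds-ratio analysis lacks its outcome whatever TyG means. If TyG is taken to be a triglyceride–glucose index (an assumption, since the protocol does not say), its triglyceride component is not scheduled either and the quartiles could not be formed.

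**4. Does a generous reading rescue the paragraph?** Suppose the retinal, renal and DN4 results count as patient characteristics. They would then be compared across 4 TyG quartiles, with both arms mixed within each. That still gives no estimate of A versus B.

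**Result:** 0 of the 2 stated analyses address the research question.

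**The case against.** The strongest reply is that the intention to compare the arms is plain from the aim and the Outcomes line, so only the method is missing, and a method may properly sit in a separate statistical analysis plan. The paragraph does not claim to be exhaustive, so such a plan could add the A-versus-B comparison without contradicting it.

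Part of this stands. The intent is clear, and a separate plan, which was not available here, could supply the comparison by addition. But the protocol is not silent on analysis. It states a specific one that does not fit its aim, design or data, and adding a correct analysis elsewhere would leave that text in force.

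Four cautions about the remedy also stand:

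- Logistic regression yields an odds ratio, so a risk difference needs a further stated step.
- Retinopathy categories appear only in the eligibility criteria; the protocol does not say that a grade is recorded at follow-up.
- It does not say how DN4 is scored.
- The second examination is timed from glycaemic control and not from allocation, so its date is unclear for a patient who does not reach target.

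These affect how the replacement is drafted. They do not alter the defect.

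**Conclusion.** The concern holds: the paragraph is wrong as written and must be fixed. Neither of its two analyses uses the randomised arm or names a microvascular outcome, and one of them has no outcome variable in the planned data. Followed literally, it gives no estimate of the effect of tight versus less tight control.

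This rests on the protocol text alone and needs no numerical assumption. No bias or loss of power is quantified: the Sample Size section gives 80 subjects without an effect size, event rate or power. If a separate plan already holds the comparison and predates any look at outcomes by arm, the consequence is milder, but the protocol text still needs correcting.

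**What to change.** Replace the paragraph by a dated amendment, made before outcomes are examined by arm:

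- **Delete** the TyG and liver-fibrosis text. Describe baseline characteristics by arm.
- **Primary analysis:** compare Group A with Group B as randomised, on one named outcome at the follow-up examination. One example is retinopathy worsening by at least one category from baseline, using the protocol's own terms (mild, moderate, severe non-proliferative, proliferative). Fit a logistic regression with arm and baseline category. The baseline factor has 2 levels, since eligibility is "Diabetic patients with mild and moderate non proliferative diabetic retinopathy". Report the risk difference with its 95% CI, obtained by standardising over the fitted model. Name a simpler fallback, such as the unadjusted risk difference, in case few patients worsen.
- **Secondary analyses,** for example: log albumin/creatinine ratio, eGFR and DN4 score by ANCOVA with arm and the baseline value, giving adjusted differences with 95% CI.
- **State** that retinopathy category is recorded at both examinations, how DN4 is scored, and from what date the 6 months run for every randomised patient.
- **Keep** the two-sided 0.05 level and attach it to the primary outcome. Handling of missing follow-up values can be left to the statistical analysis plan.

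The cost is one rewritten paragraph plus those clarifications. The underlying examinations and assays are already scheduled at both time points, so no extra patients, visits or tests are needed. The protocol dates the study from May 2022 to October 2023. If outcomes have already been seen by arm and no earlier plan holds the comparison, the new analysis must be reported as not prespecified.

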### **Statistical Package:**

Data will be analyzed with the use of IBM SPSS Statistics.

